9.4.5 Planned Interim Analysis

Preliminary analysis will be performed after 25% (10 subjects) of study sample size complete the 6-month follow-up visit.

9.5 Sample Size

The sample size is selected based on primary objective so that the study will have 80% power at the 5% significance level for testing the null hypothesis $H_0: PT \leq 0.5$ against the alternative hypothesis $H_A: PT \geq 0.75$, where PT is the true proportion of patients that will manifest a positive treatment response. As a result, the study should have 40 patients who completed the 6 months visit since this sample size will endow the test with 80.4% power at a realized significance level of 0.047 with 20% attrition, the study will need 50 subjects to reach the target sample size.

With 20% with 20% attrition, the study will need to enroll 50 patients. The PI and sub-investigators determined that increase in the sample size is necessary to evaluate the role of GAE as a disease-modifying treatment option for knee OA. Since this current study is the only active study in the U.S collecting samples for biomarker analysis and the need for a larger sample size to evaluate changes in biomarker levels, an increase in sample size is needed.

10 Source Documents and Access to Source Data/Documents

Source data is all information, original records of clinical findings, observations, or other activities in a clinical trial necessary for the reconstruction and evaluation of the trial. Source data are contained in source documents.

Examples of these original documents, and data records include: hospital records, clinical and office charts, laboratory notes, memoranda, subjects' diaries or evaluation checklists, pharmacy dispensing records, recorded data from automated instruments, copies or transcriptions certified after verification as being accurate and complete, microfiches, photographic negatives, microfilm or magnetic media, x-rays or other imaging studies, subject files, and records kept at the pharmacy, at the laboratories, and at medico-technical departments involved in the clinical trial. It is acceptable to use paper CRFs as source documents. Source CRFs can also be documented in the electronic medical record (EPIC).

The study case report form (CRF) is the primary data collection instrument for the study. All data requested on the CRF must be recorded. All missing data must be explained. If a space on the CRF is left blank because the procedure was not done or the question was not asked, write "N/D". If the item is not applicable to the individual case, write "N/A". All entries should be printed legibly in ink if paper CRFs used. If any entry error has been made, to correct such an error, draw a single straight line through the incorrect entry and enter the correct data above it. All such changes must be initialed and dated. ERRORS WILL NOT BE ERASED OR WHITED OUT. For clarification of illegible or uncertain entries, clarification will be printed above the item, then initialed and dated.

Access to study records will be limited to IRB-approved members and the study team. The investigator will permit study-related monitoring, audits, and inspections by the IRB/EC, the sponsor, government regulatory bodies, and University compliance and quality assurance groups of all study related documents (e.g. source documents, regulatory documents, data collection instruments, study data etc.). The investigator will ensure the capability for inspections of applicable study-related facilities (e.g. pharmacy, diagnostic laboratory, etc.).

Participation as an investigator in this study implies acceptance of potential inspection by government regulatory authorities and applicable University compliance and quality assurance offices.

Access to study records will be limited to IRB-approved members of the study team. The investigator will permit study-related monitoring, audits, and inspections by the IRB/EC, the sponsor, government regulatory bodies, and University compliance and quality assurance groups of all study related documents (e.g. source documents, regulatory documents, data collection instruments, study data etc.). The investigator will ensure the capability for inspections of applicable study-related facilities (e.g. pharmacy, diagnostic laboratory, etc.).

Participation as an investigator in this study implies acceptance of potential inspection by government regulatory authorities and applicable University compliance and quality assurance offices.

11 Quality Assurance and Quality Control

QC procedures will be implemented beginning with the data entry system and data QC checks that will be run on the database will be generated. Any missing data or data anomalies will be communicated for clarification/resolution.

The PI will verify that the clinical trial is conducted and data are generated, documented (recorded), and reported in compliance with the protocol, GCP, and the applicable regulatory requirements (e.g., Good Laboratory Practices (GLP), Good Manufacturing Practices (GMP)).

The investigational site will provide direct access to all trial related sites, source data/documents, and reports for the purpose of monitoring and auditing by the sponsor, and inspection by local and regulatory authorities.

12 Ethics/Protection of Human Subjects

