Methodology	Prospective, single-arm (no sham or placebo), single-center
Endpoint	
Primary Efficacy endpoint: KOOS pain score at 6-months post intervention
 
Secondary endpoints:
 
 - Rate, type, causality, and severity of adverse events (AEs) - KOOS scores at 3-, 6-, 12-, and 24-month visits - QOL index value at 3-, 6-, 12-, and 24-month visits - Pain visual analog scale (VAS) at 3-, 6-, 12-, and 24-month visits - Magnetic Resonance Angiogram (MRA) findings at 6 and 24-month visits
Study Duration	4 years
Participant Duration	Each individual subject will be enrolled for approximately 25 months to complete all study visits from the initial screening visit to last follow up at 24-months post intervention
Population	40 patients, age 30-85, of any gender, with knee pain resistant to conservative management for at least 9 months post TKA.
Study Sites	NYU Langone Health Hospitals
Number of participants	Data from 40 patients who complete 6-month visit will be required The study would enroll 50 patients to account for an attrition rate of 20%
Description of Study Agent/Procedure	Embozene™ Color-Advanced Microspheres are spherical, tightly calibrated, biocompatible, non-resorbable, hydrogel microspheres coated with an inorganic perfluorinated polymer used for embolization.
Key Procedures	GAE; a transcatheter arterial embolization of one or more genicular artery(ies) using Embozene™ Color-Advanced Microspheres

Statistical Analysis	
The primary objective is to assess the clinical success rate, which will be summarized in terms of the observed proportion of patients manifesting a positive response and a two-sided exact 95% confidence interval (CI) per the Blyth-Still-Casella method. The treatment will be declared a success if the data support the conclusion that at least 75% of treated patients show a positive response.
 
Preliminary analysis will be performed after 25% (10 subjects) of study sample size complete the 6-month follow-up visit.

----------------------	---

Schematic of Study Design

1 Introduction, Background Information and Scientific Rationale

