9.1 Statistical and Analytical Plans (SAP)

A formal SAP will not be performed prior to database lock since this study is a pilot study with no randomization.

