9.2 Statistical Hypotheses

This is a single arm study (i.e., no sham, placebo or alternative treatment included). The primary objective (clinical success rate) is a binary assessment of whether or not each patient achieved clinical success at 6 months post intervention.

The study is designed to test the null hypothesis (H_0) that the true proportion (PT) of patients that will manifest a positive treatment response, is no greater than 0.5 against the one-sided alternative hypothesis (H_A) that $PT \geq 0.75$.

The response rate will be summarized in terms of the observed proportion of patients manifesting a positive response and a two-sided exact 95% confidence interval (CI) per the Blyth-Still-Casella method (31). The treatment will be declared a success if the data support the conclusion that at least 75% of treated patients can be expected to show a positive response. The treatment will be considered unworthy of additional study without further

development if the data are consistent with the conclusion that no more than 50% of treated patients can be expected to show a positive response.

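### Section 9.5's 80.4% power and realized alpha of 0.047 do not belong to 40 completers; the implied exact test has 94.6% and 0.040

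*Combined protocol and SAP*

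**What the plan says.** Section 9.2 describes a single-arm study with a binary responder outcome at 6 months. The null is that the true response proportion "is no greater than 0.5 against the one-sided alternative hypothesis" of 0.75 or more. The same section says the result will be summarized with a two-sided exact 95% Blyth-Still-Casella interval.

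Section 9.5 opens with the design target: "The sample size is selected based on primary objective so that the study will have 80% power at the 5% significance level". It then concludes that 40 patients must complete the 6-month visit, and gives as the reason that "this sample size will endow the test with 80.4% power at a realized significance level of 0.047". Allowing for 20% attrition, it sets enrolment at 50. A following paragraph says a larger sample is needed to study biomarker changes, but it gives no biomarker calculation and no other operating characteristics for the primary test.

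Section 9.1 states: "A formal SAP will not be performed prior to database lock since this study is a pilot study with no randomization".

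**The concern.** For a single-arm binary endpoint, the null, the alternative, the sidedness, the level and the sample size fix the exact test completely. The realized alpha and the power can therefore be checked to the last digit, and the stated ones look far too low in power for 40 patients with a difference as wide as 0.5 against 0.75.

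These are the only operating characteristics given for the primary test, and no cut-off for rejection appears anywhere. Since no separate SAP is planned, Section 9.5 is where a reader will look. That reader would conclude that 40 is the number needed for about 80% power and would report a realized alpha that the test cannot have at that size. In a study of an invasive procedure, the stated reason for the number of people exposed should be the true one.

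**Working it through.** **Inputs.** Null proportion 0.5, one-sided (Section 9.2); alternative 0.75 (Sections 9.2 and 9.5); level 5% and target power 80% (Section 9.5); 40 evaluable patients, 20% attrition and 50 enrolled (Section 9.5). The phrase about a realized significance level points to an exact test, because only a discrete test has a realized level different from the nominal one.

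**Formulas.** With X responders out of n and rejection at X ≥ k:

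- realized alpha = P(X ≥ k | n, 0.5) = Σ C(n,x) 0.5^n, for x = k to n
- power = P(X ≥ k | n, 0.75) = Σ C(n,x) 0.75^x 0.25^(n−x), for x = k to n

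**Reproducing the plan's own figures.** Searching n = 5 to 200 and every cut-off for alpha that rounds to 0.047 together with power that rounds to 80.4% gives one design only: n = 23, k = 16, with alpha 0.0466 and power 0.8037. Both figures match to every stated digit. The doubled alpha there is 0.0931, so the match is with the one-sided test.

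**The same test at n = 40.**

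| Reject at | Realized alpha | Power at 0.75 |
|---|---|---|
| ≥ 25 | 0.0769 | 97.4% |
| ≥ 26 | 0.0403 | 94.6% |
| ≥ 27 | 0.0192 | 89.7% |
| ≥ 28 | 0.0083 | 82.1% |
| ≥ 29 | 0.0032 | 71.5% |

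The 5% test is k = 26. Alpha jumps from 0.077 to 0.040 without passing through 0.047, and power steps from 82.1% to 71.5% without passing through 80.4%. Neither stated figure is available at 40.

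**Other readings tried.**

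- The 50 enrolled: k = 31 gives alpha 0.0595, so the 5% test is k = 32, with alpha 0.0325 and power 97.1%.
- A random number of completers, Binomial(50, 0.8): power about 93.7%, alpha about 0.037.
- Two-sided exact test at n = 40: the doubled alphas for k = 25 to 29 are 0.1539, 0.0807, 0.0385, 0.0166 and 0.0064. None is 0.047.
- Approximate methods at n = 40 (normal with and without continuity correction, Wald, arcsine): power 94.2% to 97.8% one-sided and 88.6% to 95.5% two-sided.
- The two-sided exact 95% interval as decision tool: the shortest symmetric 95% acceptance region at 0.5 is 14 to 26 responders (coverage 0.9615). The first count that excludes 0.5 is therefore 27, with one-sided alpha 0.019 and power 89.7%.

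**What 80.4% would mean at n = 40.** Solving P(X ≥ 26 | 40, p) = 0.804 gives p ≈ 0.70, not 0.75.

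**Attrition.** 40 / (1 − 0.20) = 50, which is correct.

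**Size of the gap.** Power: 94.6 − 80.4 = 14.2 points understated. Alpha: 0.047 stated against 0.040. On the stated criterion, 23 evaluable patients already reach 80.4%. Exact power is saw-toothed, so it dips below 80% at 24, 25 and 27, but it stays above 80% at every size from 28 to 60.

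**The case against.** The best objection is that no test is named. Sections 9.2 and 9.5 give hypotheses and a level, while the only inferential tool specified for the primary outcome is a two-sided exact interval. The one-sided exact binomial test is therefore an inference. That is fair, and the fix should ask the sponsor to commit to one rule. It does not rescue the sentence, because the interval rule gives 89.7% and 0.019.

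Second, the biomarker paragraph in Section 9.5 tells the reader that the sample was enlarged for another purpose. Taken with the match at 23 patients, this makes it likely that the figures were carried over from a smaller design. That origin is inferred and nowhere stated. The paragraph does not withdraw the claim that 40 yields 80.4% power, and the section still presents 40 as the consequence of that calculation.

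Third, the error is conservative and the study is a pilot: 40 completers are more than enough for a null of 0.5, and nothing in its conduct changes. This stands, and it limits the severity.

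Fourth, a fixed 26/40 may not be the cut-off finally used. Section 9.3 admits treated participants who have completed only the 3-month visit, so the denominator may differ from 40. This also stands and is reflected in the fix.

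**Conclusion.** The concern holds. Under the hypotheses in Sections 9.2 and 9.5, 40 evaluable patients give a one-sided exact 5% test with cut-off 26, realized alpha 0.040 and power 94.6%. The stated 80.4% and 0.047 cannot be obtained at 40 with any cut-off; they are the figures for 23 patients with cut-off 16.

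This rests on an exact binomial test with exactly 40 evaluable patients and a true response of 0.75. If the two-sided exact interval decides instead, the figures are 27/40, 0.019 and 89.7%, which are also not those stated. The sample-size justification is misreported; the test is not invalidated and the enrolment target is unaffected. It should be corrected, but it does not threaten the study.

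**What to change.** Amend Section 9.5 as follows.

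1. Name the decision rule and give only its figures. For the one-sided exact test: *With 40 evaluable patients, the one-sided exact 5% test rejects the null at 26 or more responders; realized alpha is 0.040 and power is 94.6% at a true proportion of 0.75.* If the two-sided exact 95% interval is to decide, state 27 or more responders, one-sided alpha 0.019 and power 89.7%. Do not mix the two.
2. Say that the cut-off is recomputed if the evaluable number is not 40, and fix that denominator in line with Section 9.3. For example, the one-sided exact test needs 26 of 39 (alpha 0.0266, power 91.4%) or 27 of 41 (alpha 0.0298, power 93.3%).
3. Delete the claim that 40 is the size required for 80% power and state the real reason for 40. If that is the biomarker aim, say so and support it with numbers.

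A separate matter remains. The Protocol Summary says the treatment will be "declared a success if the data support the conclusion that at least 75% of treated patients show a positive response", and Section 9.2 says much the same, yet the tested null is 0.5. The corrected sentence does not settle which threshold defines success, and the sponsor should reconcile the two.

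The cost is a sentence or two and a stated rationale, by protocol amendment. Enrolment stays at 50 and data collection does not change.

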12.1 Ethical Standard

All investigators will ensure that this study is conducted in full conformity with Regulations for the Protection of Human Subjects of Research codified in 45 CFR Part 46, 21 CFR Part 50, 21 CFR Part 56, and/or the ICH E6.

12.2 Institutional Review Board

The protocol, informed consent form(s), recruitment materials, and all participant materials will be submitted to the IRB for review and approval. Approval of both the protocol and the consent form must be obtained before any participant is enrolled. Any amendment to the protocol will require review and approval by the IRB before the changes are implemented to the study. All changes to the consent form will be IRB approved; a determination will be made regarding whether previously consented participants need to be re-consented.

12.3 Informed Consent Process

12.3.1 Consent/Accent and Other Informational Documents Provided to Participants

Consent forms describing in detail the study agent, study procedures, and risks are given to the participant and written documentation of informed consent is required prior to starting intervention/administering study product. The consent form is submitted with this protocol.

12.3.2 Consent Procedures and Documentation

Informed consent is a process that is initiated prior to the individual's agreeing to participate in the study and continues throughout the individual's study participation. Extensive discussion of risks and possible benefits of participation will be provided to the participants and their families. Consent forms will be IRB-approved and the participant will be asked to read and review the document. The investigator will explain the research study to the participant and answer any questions that may arise. All participants will receive a verbal explanation in terms suited to their comprehension of the purposes, procedures, and potential risks of the study and of their rights as research participants. Participants will have the opportunity to carefully review the written consent form and ask questions prior to signing. The participants should have the opportunity to discuss the study with their surrogates or think about it prior to agreeing to participate. The participant will sign the informed consent document prior to any procedures being done specifically for the study. The participants may withdraw consent at any time throughout the course of the trial. A copy of the signed informed consent document will be given to the participants for their records. The rights and welfare of the participants will be protected by emphasizing to them that the quality of their medical care will not be adversely affected if they decline to participate in this study.

A copy of the signed informed consent document will be stored in the subject's research record. The consent process, including the name of the individual obtaining consent, will be thoroughly documented in the subject's research record. Any alteration to the standard consent process (e.g. use of a translator, consent from a legally authorized representative, consent document presented orally, etc.) and the justification for such alteration will likewise be documented.

12.4 Vulnerable Populations

12.4.1 Adults without Capacity to Consent

Subjects without capacity to consent will not be enrolled in this study. No surrogate consent will be allowed.

Since this research does not involve recruitment of individuals with impaired consent capacity, judgment that prospective subjects have the capacity to consent to the research can ordinarily be made during routine interactions with the individual during the consent process. An investigator who questions a prospective subject's capacity to consent will enroll the individual and should consult with the IRB.

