4.1 Inclusion Criteria

In order to be eligible to participate in this study, an individual must meet all the following criteria:

1. 30-85 years of age, of any gender
2. Knee pain resistant to conservative treatment for at least 9 months* post TKA performed for knee OA
3. Moderate to severe knee pain: pain VAS ≥ 40 mm
4. Willing, able, and mentally competent to provide informed consent and complete study questionnaires in English. The validated KOOS study questionnaires are only available in English.

* Conservative management is defined for the purpose of this study as use of analgesics (anti- inflammatory drugs, acetaminophen), or physical therapy and muscle strengthening exercises); 9-month duration of pain was selected because this time interval is adequate for knee pain to be considered refractory to conservative care.

Note: If both knees meet criteria, the one with a higher VAS score will be selected for the study (i.e., target knee).

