4.3 Vulnerable Subjects

The study does not intend to recruit vulnerable subjects. The study will not recruit any children, pregnant women, or prisoners.

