12.4.2 Surrogate Consent

Surrogate consent will not be allowed in this study.

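### Section 12.4.1 tells an investigator who doubts a subject's capacity to consent to enrol that subject, contradicting its own opening ban and inclusion criterion 4

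*Combined protocol and SAP*

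**What the plan says.** Section 12.4.1 gives two instructions that do not fit together. Its first sentence is a flat ban: "Subjects without capacity to consent will not be enrolled in this study". Its second paragraph starts from the premise "Since this research does not involve recruitment of individuals with impaired consent capacity" and leaves capacity to be judged in the ordinary course of the consent conversation. It then closes with the rule for a doubtful case: an investigator in doubt about a prospective subject's "capacity to consent will enroll the individual and should consult with the IRB".

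The related provisions all lean towards the ban:

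- Section 4.1, criterion 4, requires each participant to be "Willing, able, and mentally competent to provide informed consent and complete study questionnaires in English", and every inclusion criterion must be met.
- Section 4.3 states: "The study does not intend to recruit vulnerable subjects".
- Section 12.4.2 states: "Surrogate consent will not be allowed in this study". Section 12.4.1 says the same.

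One further provision sits awkwardly with these. Section 12.3.2 gives consent from a legally authorized representative as an example of a change to the standard consent process that is to be documented and justified.

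**The concern.** The closing sentence of 12.4.1 is an operative instruction, and it is the only one for the moment when capacity is in question. No formal capacity assessment is described that would settle the matter by another route.

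The stake is participant protection. The intervention is investigational and is done under an IDE (section 1.2). It involves femoral arterial access (section 5.2) and non-resorbable microspheres (section 1.2). The risks listed in section 1.4.1 include limb-threatening ischemia and, very rarely, death. Consent to such a procedure should not rest on unresolved capacity.

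Several people may rely on the sentence. Section 4.4 allows a coordinator or co-investigator to guide consent, and section 6.3.1 allows screening in any of three types of clinic. Sections 7.8 and 8 make the PI, who is also the sponsor, responsible for safety oversight and for monitoring. The protocol describes no independent monitor who would be placed to notice a wrong enrolment.

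**Working it through.** No arithmetic applies. The claim depends on no error rate, effect size, attrition rate or sample size, so the check is to set the provisions side by side.

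| Question | Provision | Answer |
|---|---|---|
| May a person without capacity be enrolled? | 12.4.1, first paragraph | No |
| Is competence to consent a condition of entry? | 4.1, criterion 4 | Yes |
| Can someone else consent instead? | 12.4.1 and 12.4.2 | No |
| What happens when capacity is questioned? | 12.4.1, last sentence | Enrol, and the IRB should be consulted |
| Must the IRB answer before enrolment? | No provision found | Not stated |

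1. **Force of the two verbs.** Enrolment is expressed with *will* and consultation with *should*. Enrolment is therefore the firm instruction. The consultation is advisory, and no order in time is set.

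2. **Against criterion 4.** While capacity is in doubt, competence has not been established, so the criterion is not yet shown to be met. Enrolling at that point conflicts with it, whatever the later answer.

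3. **Against the opening ban.** The ban covers people who lack capacity; the last sentence covers people whose capacity is questioned. The groups overlap. For those in the overlap, the last sentence directs an enrolment that the first forbids. For the rest, it directs enrolment before anyone knows which group they are in.

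4. **Search for a correction elsewhere.** None was found. Section 12.3.2 requires a signature before study procedures but sets no capacity test. The exclusion criteria in 4.2 do not mention capacity. Section 4.3 names children, pregnant women and prisoners, but not adults with impaired capacity. Section 12.2 governs IRB approval of documents and amendments, not individual doubtful cases.

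5. **Consequence for the investigator.** Following the last sentence departs from criterion 4, while declining to enrol departs from the last sentence. Section 13.3 treats any noncompliance with the protocol as a deviation, so neither course is clean.

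6. **Section 12.3.2 against 12.4.** Documenting consent by a representative as a possible alteration presupposes that such consent could be accepted. Both 12.4.1 and 12.4.2 say it cannot. This is a second, smaller conflict on the same subject.

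**The case against.** The best reply is that this is a slip that nobody would act on. A missing *not* would explain the sentence, everything around it points to non-enrolment, and enrolling someone found to lack capacity would still breach both the ban and criterion 4. Much of this stands. The surrounding text makes literal use less likely, and nothing suggests that the sponsor chose the rule deliberately. But the missing word is an inference. The sentence as printed is grammatical and can be followed, and no other provision tells the investigator what to do while the doubt lasts.

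Three stronger readings are tempting, and the documents do not support them:

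- A reader might infer that the sentence enrols precisely the people whom the protocol excludes. It does not. Questioned capacity is not the same as absent capacity, and some of those questioned will have it.
- A reader might infer that consent from each such person would be invalid. Doubt is not proof of incapacity. The consent would be in question, and invalid only if capacity was in fact lacking.
- A reader might infer that the KOOS and VAS results are compromised because they are self-reported. The documents show no such effect, and criterion 4 separately requires that participants be able to complete the questionnaires.

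**Conclusion.** The contradiction is real and the sentence is wrong as written. It directs enrolment while capacity is unresolved, makes IRB consultation advisory and unsequenced, and leaves no surrogate route. That conflicts with the opening of 12.4.1 and with criterion 4.

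Its size cannot be put as a number, because the documents give no frequency of doubtful cases. For any one case, the validity of consent to an invasive investigational procedure would be in doubt. The target of 40 patients completing the 6-month visit, the enrolment of 50, the power calculation and the planned analyses are all untouched.

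The case for correction therefore rests on participant protection alone. It assumes that the printed sentence is the current protocol text; the extracted section shows no gap or redaction.

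**What to change.** Amend the last sentence of 12.4.1 to agree with that section's first paragraph and with criterion 4. For example: an investigator who questions a prospective subject's capacity will not enroll the individual and should consult with the IRB, and no enrolment takes place unless capacity is established. The final clause matters because changing one word alone would not say whether someone later judged capable may enter.

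In the same amendment, reconcile the reference in 12.3.2 to a legally authorized representative with the bar on surrogate consent in 12.4.1 and 12.4.2.

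The only cost is a small protocol amendment, which under section 12.2 needs IRB review and approval before it takes effect. Study procedures, visits and data collection do not change.
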